Title: Repeated TMS at Low Frequencies to Reduce Seizure

NCT Number: NCT03154307

Protocol Number: 15-135

Document Date: September 21, 2021

Repeated TMS at Low Frequencies to Reduce Seizure Occurrence

I. SUMMARY OF THE RESEARCH

Perform non-invasive neuro-navigated repeated Transcranial Magnetic Stimulation (rTMS) at low frequencies (LF) with the intent to reduce the occurrence of seizures over time. Seizure reduction and improvements in the quality of life in patients with epilepsy will be associated with increased cortical inhibition resulting from the LF-rTMS sessions over time. This procedure using rTMS at low frequencies (LF-rTMS) between 0.5 and 1 Hz is a safe and painless method for noninvasive focal cortical brain stimulation, which will be evaluated in its efficacy at reducing/suppressing seizures. Accordingly, we propose a clinical trial in patients with epilepsy to test whether LF-rTMS can improve seizure suppression. The location of the presumed 3D source in the brain will be stimulated for few minutes (10 to 15mns). With the same rTMS modality, we will also perform motor threshold mapping in conjunction with its fully integrated and compatible electroencephalography (EEG) module.

Despite the progress made in the development of multimodal imaging algorithms, there are still limitations and drawbacks to be overcome in the area of time and space alignments. The simultaneous use (time alignment) of different recording modalities on a same patient (space alignment) would validate a given outcome as long as it is imaged or recorded in more than one imaging/recording modality. As such, brain mapping and 3D source localization are consolidated in a same 3D space and in context to the 3D source where seizures are anticipated to emanate from. The multimodality structure relies in the simultaneous use of TMS, MRI, EEG and Electromyography (EMG), all non-invasive, safe, and FDA approved. The complete procedure will include tasks of motor threshold mapping using non-invasive brain navigated magnetic stimulation, while simultaneously monitoring EEG and EMG. The study is of minimal risk with common risks/discomforts of the test limited to mild and brief discomfort of the skin on the scalp from the Velcro strap or the EEG electrodes. Also, occasional side effects of the test are minor and brief headache from prolonged TMS stimulation.

The significance of this work is related to addressing the effectiveness of long-term use of rTMS for medically refractory patients (failed two or more medications) as a non-invasive alternative to other established techniques (i.e. VNS, RNS, among others). For this purpose, we will unify data from different sources whose analysis and results are strengthened and validated in more than one modality (TMS, MRI, EEG in consortium), which will secondarily provide higher resolution for assessing the dysfunction in both temporal and spatial domains. All of these steps are to ensure the delivery of the most effective rTMS brain stimulation with the intent to reduce/suppress the occurrence of seizures in patients with epilepsy to include both children and adult populations.

II. SCIENTIFIC BACKGROUND & LITERATURE REVIEW

Transcranial Magnetic Stimulation with both single (sTMS) and repetitive simulation (rTMS) capabilities is a non-invasive technology, which serves not only as a powerful tool for mapping the eloquent cortex of the brain, but provides great potential for treatment and eliciting new insights into a variety of brain disorders, especially for patients who do not benefit from drug treatments. The TMS technology was introduced in the 1980s, and since then, it has been used in clinical care for several neurological disorders [1–4]. The initial intent of this technology was to improve the health of patients with depression as exemplified in studies [5–8]. Its application has now been

Repeated TMS at Low Frequencies to Reduce Seizure Occurrence

extended to gauge the merits of magnetic stimulation to other neurological disorders such as epilepsy [9–11], Huntington’s disease [12], Parkinson’s disease [13], different effects of schizophrenia [14–16], Alzheimer’s disease, and effects of aging [17, 18], in patients who have had a stroke [19–21], autism [22, 23], and attention deficit and hyperactivity disorders [23, 24]. These are by no means an exhaustive listing of such noteworthy references, but these are examples of studies that highlight the extensive use of TMS technology. It should be noted that the use of TMS can be performed under two modes of operation, namely, single pulse [25] or repetitive mode of stimulation [26, 27].

The hypothesis is that low frequency brain stimulation focused on and around the seizure onset zone will reduce the occurrence of seizures over time. We base this hypothesis on clinical trials and reports on the treatment of seizures reported in the literature. It has been shown that high frequency rTMS, although beneficial in the treatment of patients with depression, can actually cause seizures [28], while low-frequency rTMS has the opposite effect in that it can actually inhibit the occurrence of such seizures. Modulating brain activity is shown to depend on the selection of the frequency used during stimulation [29, 30]. Therefore, and on the basis of this knowledge, we will restrict the brain stimulation process to a low frequency range between 0.5 and 1 Hz rTMS in people with focal and generalized epilepsy, while taking into consideration all the safety guidelines, ethical issues, and required precautions from prior research in the use of TMS technology [31, 32, 33].

The significance of this work is to address the efficacy of the long-term use of rTMS in the treatment of refractory epilepsy patients. Additionally, the integration of multimodal imaging where TMS, MRI, and EEG could provide data not available through DCS or fMRI alone, which in turn can only augment our understanding of brain mapping and brain dynamics. This study will employ a carefully planned low frequency rTMS protocol, with therapeutic sessions over a one-year time frame, with a possible extension phase protocol if initial study is successful.

III. RESEARCH OBJECTIVES

1. To reduce/suppress the number of seizures in patients with medically intractable epilepsy (partial and generalized) with the use of long-term LF-rTMS. Stimulation will be applied with determined seizure onset zone by inverse solutions and 3D software algorithms of analysis of electroencephalographic data. This objective is based on promising rTMS studies that reported reductions in seizure frequency. The primary continuous outcome measures for this aim will be seizure frequency, EEG epileptiform discharge frequency, seizure severity scale, and psychometric testing.
2. Statistical analysis will be conducted using ANOVA and secondary outcome measures will analyze the number of patients whose seizure frequency decreases by at least 50% (e.g., the “responder” threshold used in studies of anticonvulsant efficacy).
3. Localize through TMS stimulation motor threshold cortex mapping of the abductor pollicus brevis-evoked response. This is an important step for determining the appropriate patient-specific stimulation threshold.
4. Measure EEG alpha asymmetry before and after rTMS and compare the change in this continuous variable among treatment and sham groups in intractable epilepsy. We

Repeated TMS at Low Frequencies to Reduce Seizure Occurrence

hypothesize, that rTMS will alter the ratio of right to left EEG alpha power (8-13 Hz). Alpha asymmetry is known to be common in patients with epilepsy in contrast to healthy controls where alpha symmetry is seen as more prevalent.

IV. INCLUSION AND EXCLUSION CRITERIA

All individuals between ages 18 to 80 that are medically refractory who have completed informed consent/assent, and able to cooperate with non-sedated navigated TMS testing will be included. Exclusion criteria include the presence of implanted electronic devices (e.g., pacemaker, medication pump, brain or vagus nerve stimulator, cochlear implant), intracranial metal (e.g., aneurysm clip), or inability to cooperate with the rTMS session.

Goal recruitment will be 90 epilepsy patients, based on the following:

- At least 3 seizures in one month
- No status epilepticus for 1 year
- No change in medication for 1 month

V. METHODS AND ACTIVITIES

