-----------	-----------	---------	----------	------	----------	-------

Repeated TMS at Low Frequencies to Reduce Seizure Occurrence

						Design
1Hz	120%MT	800	5 days/week for 2 weeks 1/week for 1 month 1/month for 11 months	8	3D Source Localization, vertex, and bipolar frontal	double-blinded, sham-controlled
1Hz	120%MT	800	5 days/week for 2 weeks 1/week for 1 month 1/month for 11 months	8	coil will be placed with an angle of 45 degrees with respect to the scalp without direct contact	double-blinded, sham-controlled

Using a single-blinded, sham-controlled design, we will screen patient's age 2 to 80 years with focal and generalized intractable epilepsy. Baseline data will include a detailed seizure diary over 4 weeks, psychometric testing/neuropsychology evaluation, and 20-minute EEG recordings. Each patient will then begin treatment with 14 minute sessions of 1 Hz rTMS or sham rTMS, 120%MT, and 800 stimuli on the position of the calculated 3D source using EEG, MRI, and digitized electrode locations. The protocol will be divided in 3 groups (Groups 1, 2 and 3) as follows:

- Groups 1, 2, and 3: LF-rTMS for 2 weeks (5 days per week for total of 10 days).
- Group 1: protocol total duration: 1 year: LF-rTMS 1 session/week for 1 month (4 days), and LF-rTMS 1 session/month for 11 months
- Group 2: protocol total duration: 1 year: LF-rTMS 1 session/month for 12 months
- Group 3 (placebo protocol, total duration: 1 year): LF-rTMS 1 session/week for 1 month (4 days); and LF-rTMS 1 session/month.

During each session EEG will be recorded. Also, we would update number of events and frequency data from ongoing seizure diary. Psychometric testing will be performed at the beginning of study, 3 months, and at the end of the study. Thus, each patient will have rTMS testing, psychometrics, and EEG recordings.

Goal recruitment will be 90 medically refractory participants, with 30 participants for each of the three groups, based on the following:

- At least 3 seizures in one month
- No status epilepticus for 1 year
- No change in medication for 1 month

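### Objective 1 names four primary outcomes with no lead outcome, alpha, multiplicity adjustment or success rule, and two of the four are not fully specified

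*Combined protocol and SAP*

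**What the plan says.** The hypothesis in Section II is about seizures: "low frequency brain stimulation focused on and around the seizure onset zone will reduce the occurrence of seizures over time". Section III, item 1 then gives this aim four primary outcomes: "The primary continuous outcome measures for this aim will be seizure frequency, EEG epileptiform discharge frequency, seizure severity scale, and psychometric testing". Item 2 supplies the method and one secondary outcome, a 50% responder count: "Statistical analysis will be conducted using ANOVA and secondary outcome measures will analyze the number of patients whose seizure frequency decreases". Item 4 adds a separate comparison without giving it a rank: "Measure EEG alpha asymmetry before and after rTMS and compare the change in this continuous variable among treatment and sham groups".

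Section 5.3 sets the assessments. At baseline: "Baseline data will include a detailed seizure diary over 4 weeks, psychometric testing/neuropsychology evaluation, and 20-minute EEG recordings". During follow-up: "During each session EEG will be recorded. Also, we would update number of events and frequency data from ongoing seizure diary". And: "Psychometric testing will be performed at the beginning of study, 3 months, and at the end of the study". The same section has three groups of 30 patients, two active and one placebo: "The protocol will be divided in 3 groups (Groups 1, 2 and 3) as follows".

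Section VI names the software, derives seizure frequency from weekly averages taken before and after treatment, and sorts patients into an rTMS group and a placebo group. It gives no alpha, model, contrast or decision rule. The nearest thing to a success criterion is in Section VIII, where an undefined medical improvement triggers the offer of an extension phase.

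**The concern.** With four outcomes sharing the label primary and no rule linking them, a reader cannot tell in advance which result would make the trial positive. As written, a difference in EEG discharges or in a psychometric score could be presented as a primary success even if seizures did not fall, which is not the stated hypothesis. If one success out of four is enough, the chance of a false positive claim also exceeds that of a single test.

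Two of the four outcomes cannot be analysed from the text alone. The severity scale has neither an instrument nor a time point. Psychometric testing has time points but no named test or score, so it could yield several results to choose from. Seizure frequency has a derivation, but its post-baseline period is open: sessions run for a year, and Section 5.3 describes no diary period after the last one.

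**Working it through.** The plan states no alpha, power or error rate, so there is no figure of its own to reproduce.

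**Specification of each primary outcome**

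| Outcome | Assessment time (5.3) | Instrument or score | Derived variable (VI) |
|---|---|---|---|
| Seizure frequency | 4-week baseline diary, then ongoing | diary | weekly average, window not fixed |
| EEG discharge frequency | baseline and each session | EEG | none |
| Psychometric testing | start, 3 months, end | none named | none |
| Seizure severity scale | none stated | none named | none |

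**Inputs for the error rate**

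- From the documents: k = 4 primary outcomes, or k = 3 if only those with scheduled assessments are counted; rTMS pooled against placebo, 60 versus 30.
- Assumed: each outcome tested once at two-sided 0.05, so 0.025 in the direction favouring rTMS; any one success suffices; common pairwise correlation ρ from 0 to 0.7.

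**Independent outcomes:** 1 − (1 − 0.025)^k.

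- k = 4: 1 − 0.975^4 = 0.0963
- k = 3: 1 − 0.975^3 = 0.0731

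**Correlated outcomes:** 1 − ∫ φ(u) · Φ((1.96 − √ρ·u)/√(1 − ρ))^k du, by numerical integration.

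| ρ | k = 3 | k = 4 |
|---|---|---|
| 0 | 7.3% | 9.6% |
| 0.3 | 6.8% | 8.7% |
| 0.5 | 6.3% | 7.8% |
| 0.7 | 5.5% | 6.5% |

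Simulated t tests with 60 versus 30 patients (100,000 runs, k = 4) gave 9.8%, 8.7%, 8.0% and 6.6%, in agreement.

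**Unnamed psychometric score.** If testing produced two scores, making k = 5, the range would be 11.9% at ρ = 0 to 7.4% at ρ = 0.7.

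**Open window.** Naming seizure frequency alone would not secure 2.5% if the window could be chosen afterwards. With the same formula at ρ = 0.5, 0.7 and 0.9, a choice between two windows gives 4.5%, 4.2% and 3.5%; a choice among three gives 6.3%, 5.5% and 4.2%.

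**Price of keeping four primaries.** Bonferroni at 0.05/4 = 0.0125 two-sided gives 1 − (1 − 0.00625)^4 = 2.48% at ρ = 0. The difference detectable with 80% power (two-sample t test, 60 versus 30) rises from 0.63 to 0.76 SD.

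**The case against.** The strongest reply is that seizure frequency is the lead outcome in all but name. It is listed first, it is the subject of the hypothesis and of the responder analysis, and it alone has a derivation. The four outcomes are joined by a conjunction, and the plan nowhere says that one success is enough. If all four had to succeed there would be no inflation. This stands as a limit on the percentages. It does not remove the defect, because the plan adopts neither reading.

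A reader might infer that the severity scale will not be collected, since the Section VI data list omits it. The documents do not support that. The list covers MRI, EEG, stimulation maps and EMG, and it also omits the diary and psychometric testing, which Section 5.3 schedules. It is therefore not exhaustive. A severity scale might also sit within the health questionnaire in Section VI or the unspecified psychometric evaluation. What the text shows is that no instrument or time is stated.

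A reader might also count alpha asymmetry as a fifth primary outcome. Section III limits the word primary to the aim in item 1. Alpha asymmetry is a separate, unranked objective.

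**Conclusion.** The concern holds. It is certain from the text that four outcomes are called primary with no alpha, lead outcome, adjustment or success rule; that the severity scale lacks an instrument and an assessment time; that psychometric testing lacks a named test or score; and that the seizure-frequency window is not fixed. This goes beyond missing detail, because it decides what the trial may claim.

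The size is conditional. With two-sided 0.05 per outcome, any one sufficing, and correlation from 0 to 0.7, the chance of a false result favouring rTMS is 9.6% to 6.5% for four outcomes and 7.3% to 5.5% for three, against 2.5% for one. These are two separate ranges; taking 5.5% as the lower end for four outcomes would be wrong. They could be too low if psychometric testing yields several scores. A reader might take them as the trial's actual error rate, but the documents do not support that, because they state neither the alpha nor the success rule on which the figures depend.

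**What to change.** Before unblinding, amend Section III, item 1 and Section VI to name one primary outcome: change in average weekly seizure frequency from the 4-week baseline diary, rTMS versus placebo, at two-sided 0.05. State three further things:

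- one change scale (absolute, percentage or log);
- one test or model;
- one fixed window. An example is from the end of the 2-week course common to all groups to the end of the year. Maintenance sessions continue through that window in every group, so the plan should say so and the before/after derivation in Section VI should be reworded to match.

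Make EEG discharge frequency, one named psychometric score at one named time, and the 50% responder rate secondary. Either test them with Holm over the actual number of tests (smallest p against 0.05/3 = 0.0167 for these three, or 0.05/4 = 0.0125 with severity added) or report estimates with confidence intervals. State that alpha asymmetry is not primary.

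Name the severity scale and schedule it at the psychometric time points as a secondary outcome, or delete it if baseline scores can no longer be collected. The documents do not give enrolment status.

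A fixed sequence starting with seizure frequency, or Bonferroni over four fully specified primaries, would also control the error. Bonferroni has the loss of sensitivity shown above, so a single primary is preferable.

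The cost is wording, plus one scale at three existing time points if severity is kept. The downside is that a positive EEG, severity or psychometric result alone could no longer be called a primary success.

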5.1 Interventions and Interactions of the Research Study

An Informed Consent will be obtained by Baptist Health personnel and the subject will be explained the aims and procedures of the research task that will be performed by FIU personnel.

- Positioning of the subject in the TMS chair along with the registration apparatus (spectacles or head band) and performing a high-resolution (< 2mm) registration of the subject head to the pre-acquired magnetic resonance imaging (MRI) since the TMS machine is MRI-guided.
- Connecting 1-6 EMG surface electrodes on target muscles to evaluate muscle response to TMS stimulation, and
- EEG electrodes will be placed according to the 10-20 system montage.

The systems (EMG and EEG) will continuously record the activity from the subject throughout the procedure. It should be noted that since these acquisition techniques, which are completely non-invasive and used regularly in clinical settings, render little or no discomfort to the test subjects. There will be a neurologist ([name]) on the premises during all procedures. Sections 5.1-5.3 and 5.4.3-5.4.4 of the “Methods and Activities”, as explained below will be performed completely by FIU personnel ([name]. and [name]). [name]. from FIU will supervise all the protocol outcomes. [name] will refer all epileptic patients that will be included in this study research. Also copies of standard care MRI images (not taken as part of this study) will be provided by Baptist Hospital Radiology Department after enrolled subjects sign a HIPAA agreement to allow it.

5.2 TMS mapping and recording

The technology used in this research study is based on the so-called Neuro-navigated Brain Stimulation (NBS), a technology developed for mapping the eloquent cortex of the brain as well for therapy as currently used on different neurological disorders in different centers and healthcare

Repeated TMS at Low Frequencies to Reduce Seizure Occurrence

providers. This newly acquired technology by the CATE center is to improve accuracy in the diagnosis and in improving mapping the brain non-invasively. TMS mapping and recording will allow for (1) MRI-guided neuro-navigation with electric-field controlled stimulation to precise 3D targets in the cortex; (2) powerful and highly focal magnetic stimulator and coils with the ability to monitor the point of focality as well depth attenuation; (3) a compatible fully integrated EMG for motor functions; and (4) a compatible 60-channel EEG module for integrating brain electrical activities at rest and under the TMS stimulation process. TMS thus offers a non-invasive alternative to DCS (gold standard). This can be further augmented with the fMRI images in order to validate the location of these eloquent cortical areas.

Since the TMS is FDA approved for motor threshold mapping, the following protocol is used to map the eloquent cortex.

5.2.1 Motor Threshold Mapping Protocol

All the patients will lie down in a comfortable chair in a supine position. The Nexstim system's 6-channel EMG module (SR=1450 Hz, cut-off frequency of 350 Hz for the low pass filter) will automatically calculate the motor evoked potential (MEP) amplitudes and latencies as the motor cortex (cortex area of the thumb) is stimulated. Disposables Ag-AgCL surface electrodes will be used to record the MEP responses displayed in a computer screen in order to assess the validity of the response based on the strength of MEPs, reflecting the ability of that area to develop a muscle contraction.

This protocol will consist of the following two steps:

- Perform TMS in order to determine the motor threshold for each individual patient.
- In order to obtain the motor threshold, the intensity of the TMS is gradually increased in order to elicit responses from the Abductor Pollicis Brevis (APB) muscle near the thumb.
- Once the motor threshold is determined the complete tracking of the motor cortex is carried out at an intensity of 10% greater than the motor threshold.
- The entire process of motor cortex mapping is estimated to take 15-20 minutes.

Prior studies have demonstrated that partial motor threshold can vary in a person from session to session and for this reason, it will be performed every time patients are treated.

5.3 Epilepsy Protocol for rTMS at low frequencies in Epilepsy (long-term protocol)

Repetitive transcranial magnetic stimulation (rTMS) at low frequency range (0.5-1 Hz), LF-rTMS is a safe and painless method for noninvasive focal cortical brain stimulation which is efficacious in suppressing seizures. Accordingly, we propose a clinical trial in patients with epilepsy to test whether LF-rTMS can improve seizure reduction/suppression. The location of the presumed 3D source in the brain and its immediate surroundings will be stimulated for 14 minutes at these low frequencies.

Repeated TMS at Low Frequencies to Reduce Seizure Occurrence

Existing protocols that are related to this work [34-41] are listed in Table 1. These were reviewed in order to bring in synergy the strengths of each for carrying out safe and effective rTMS sessions. Accordingly, we propose a long term trial in patients with focal and generalized epilepsy, to test whether LF-rTMS can reduce/suppress the occurrence of seizures, and determine for how long such outcomes can last for each patient. The proposed protocol that will be followed in this study is described in Table II on the basis of the knowledge gained from these previous studies.

Table 1: Existing Protocols.

Cited Literature	Frequency	Threshold	Stimuli	Schedule	Coil	Outcome-seizures	Position	Daily Stimulation time
Cantello, et al. 2007 [34]	0.3 Hz	100%MT 65%MSO	500/train	2 trains/day For 5 days	0	No change	vertex	28 min.
Fregni, et al. 2006 [35]	1Hz	70%MSO	1200/train	1 train/day For 5 days	8	Decreasing	3D source vertex	20 min.
Theodore, et al. 2002 [36]	1 Hz	120% MT	900/train	2 trains/day For 1 week	8	Decreasing	3D source	15 min.
Tergau, et al. 2003 [37]	0.33, 1 Hz	Below MT	1000/Train	1 train/day For 5 days	0	Decreased 0.33 Hz	vertex	55 min. 17 min.
Brasil-Neto, et al. 2004 [38]	0.5 Hz	90% MT	100/train	Biweekly / 4 weeks	8	Decreased	3D source vertex	3 min.
Misawa, et al. 2005 [39]	0.5 Hz	90%MT	100	Single session repeated at 3 months	8	Decreased for 2 months	3D source	3 min.
Menkes, et al. 2000 [40]	0.5 Hz	95%MT	20/train	5 trains/day Biweekly for 3 months	0	decreased	3D source	0.6 min.
Rossi, et al. 2004 [41]	1 Hz	90% rMT	900	Single session	8	decreased	3D source	15 min.

MT: Motor threshold, MSO: Maximum stimulator output

Table 2: Suggested Long-Term Protocol for this Study: Treatment vs. Placebo Groups
(Stimulation time: 14 minutes)

Frequency	Threshold	Stimuli	Schedule	Coil	Position	Study
-----------	-----------	---------	----------	------	----------	-------

Repeated TMS at Low Frequencies to Reduce Seizure Occurrence

						Design
1Hz	120%MT	800	5 days/week for 2 weeks 1/week for 1 month 1/month for 11 months	8	3D Source Localization, vertex, and bipolar frontal	double-blinded, sham-controlled
1Hz	120%MT	800	5 days/week for 2 weeks 1/week for 1 month 1/month for 11 months	8	coil will be placed with an angle of 45 degrees with respect to the scalp without direct contact	double-blinded, sham-controlled

Using a single-blinded, sham-controlled design, we will screen patient's age 2 to 80 years with focal and generalized intractable epilepsy. Baseline data will include a detailed seizure diary over 4 weeks, psychometric testing/neuropsychology evaluation, and 20-minute EEG recordings. Each patient will then begin treatment with 14 minute sessions of 1 Hz rTMS or sham rTMS, 120%MT, and 800 stimuli on the position of the calculated 3D source using EEG, MRI, and digitized electrode locations. The protocol will be divided in 3 groups (Groups 1, 2 and 3) as follows:

- Groups 1, 2, and 3: LF-rTMS for 2 weeks (5 days per week for total of 10 days).
- Group 1: protocol total duration: 1 year: LF-rTMS 1 session/week for 1 month (4 days), and LF-rTMS 1 session/month for 11 months
- Group 2: protocol total duration: 1 year: LF-rTMS 1 session/month for 12 months
- Group 3 (placebo protocol, total duration: 1 year): LF-rTMS 1 session/week for 1 month (4 days); and LF-rTMS 1 session/month.

During each session EEG will be recorded. Also, we would update number of events and frequency data from ongoing seizure diary. Psychometric testing will be performed at the beginning of study, 3 months, and at the end of the study. Thus, each patient will have rTMS testing, psychometrics, and EEG recordings.

Goal recruitment will be 90 medically refractory participants, with 30 participants for each of the three groups, based on the following:

- At least 3 seizures in one month
- No status epilepticus for 1 year
- No change in medication for 1 month

In retrospect, promising rTMS studies have reported reductions in seizure occurrence [35, 42-54]. Several studies [45-48] included children, and reported improvement in seizure occurrence in the majority of these children, due to a modulation in cortical excitability, induced by low frequency rTMS. Other studies measured EEG alpha asymmetry [49] before and after rTMS to assess the change in this continuous variable among treatment and sham groups in intractable epilepsy. In these studies, it is hypothesized that rTMS could alter the ratio of right to left EEG alpha power

Repeated TMS at Low Frequencies to Reduce Seizure Occurrence

(8-13 Hz). Alpha asymmetry is known to be present in patients with epilepsy in contrast to healthy controls. The major objective in all of these studies is to seek seizure reduction associated with increased cortical inhibition resulting from the LF-rTMS sessions [34, 50-53]. TMS (single or repetitive pulse) thus offers a noninvasive option that could serve as a therapeutic tool that will reduce the occurrence of seizures.

